In the event that any subject acquires an inhibitor to FVIII, Immune Tolerance Induction (ITI) will be offered. The subject may receive BAY 81-8973 up to 200 IU/kg daily or 100 IU/kg twice a day for 18 months. Treatment will be at the discretion of the treating physician, although the detailed treatment plan should be agreed with the Coordinating Investigator (as of Amd 7). Subject commences on ITI therapy will be followed up within the extension study. Data on treatment, FVIII measurements, and inhibitor levels will be collected. (as of Amds 1 and 6)

Primary variable

Annualized number of total bleeds (sum of spontaneous bleeds and trauma bleeds) within 48 hours (h) after a prophylactic infusion. (as of Amd 1)

Justification of the design

The study is designed according the requirements defined in the European "Note for Guidance on the clinical investigation of recombinant FVIII and FIX products" CPMP/BPWG/1561/99 and taking into account the revised draft version of this guideline CHMP/BPWP/144533/09⁽¹⁶⁾ (Committee for Proprietary Medicinal Products/Blood Products

Working Group; Committee for Medicinal Products for Human Use/Blood Products Working Party).

End of study

For each participating European Union (EU) country, the end of the study according to the EU Clinical Trial Directive will be reached when the last visit of the last subject (including subjects in the extension study) for all centers in the respective country has occurred.

The end of the study as a whole will be reached as soon as the end of the study according to the above definition has been reached in all participating countries (EU and non-EU).

The primary completion date for this study according to the Food and Drug Administration (FDA) Amendment Act is specified in a separate document (not part of this Clinical Study Protocol [CSP]).

5. Study population

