7.3 Efficacy

7.3.1 Efficacy variables

The primary variable is the annualized number of **total bleeds (sum of spontaneous bleeds and traumatic bleeds) during prophylaxis that occurs** within 48 h **of the last prophylaxis infusion. Both joint and non-joint bleeding will be assessed. (as of Amd 1)** Additional efficacy parameters include:

- Subject/parents' assessment of the response **to** treatment of bleeding events, which is assessed as excellent, good, moderate or **poor. (as of Amd 1)**
- Annualized number of **total bleeds (sum of spontaneous and trauma bleeds) (as of Amd 1)** during prophylaxis treatment
- Assessment of **adequacy of hemostasis (as of Amd 1)** during surgical interventions
- Number of infusions for the treatment of a bleed
- Consumption of FVIII

The main surrogate efficacy parameter is the **recovery of FVIII after infusion. (as of Amd 1)**

If an infusion is given to control a bleed at the same location within 72 hours of the previous dose for a bleed at that site, it is to be considered a follow-up infusion and not treatment of a new bleed, unless both bleeds are skin/mucosa bleeds (as of Amd 3).

The complete list of variables to be analyzed for this study will be provided in the Statistical Analysis Plan.

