Efficacy data will be summarized for all subjects in the *intent-to-treat (as of Amd 1)* (ITT) population. The primary efficacy variable will be the annualized number of *total bleeds (sum of spontaneous bleeds and traumatic bleeds) (as of Amd 1)* within 48 h after a prophylaxis infusion *(as of Amd 1)*. Other variables summarized will be the physician's/subject's/parents' *(as of Amd 1)* assessment of the response to treatment of bleeds (excellent, *good, moderate, poor*) *(as of Amd 1)* and during surgeries. The number of treatments required to control bleeds, the *proportion (as of Amd 1)* of prophylaxis infusions with less than expected therapeutic effect (LETE) (defined as a prophylaxis infusion followed by a bleed within 48 h), annualized number of *total bleeds (sum of spontaneous bleeds and trauma bleeds) (as of Amd 1)* during prophylaxis, FVIII usage and recovery will be summarized. *A detailed Statistical Analysis Plan will be provided (as of Amd 1).*

Pharmacokinetics / pharmacodynamics (Optional)

For investigation of drug exposure and potential relationships to drug effects, selected subjects will participate in pharmacokinetic (PK) sampling. Any subject's participation in PK sampling is voluntary and consent/*assent is required (as of Amd 1)*.

Based on the known PK of FVIII in hemophilia subjects it is expected that a *reduced (as of Amd 1)* sampling strategy will be sufficient to calculate relevant pharmacokinetic parameters.

Blood samples for population PK analyses will be collected according to a sampling schedule. Blood sampling for the determination of FVIII:C in plasma will be taken at baseline *before the infusion (pre-infusion)* at 20-30 minutes, *4 h, and 24 h* after end of *infusion*. *Attempt should be made to collect the sample as close as possible to the times indicated above. If there is a delay in collecting a sample, the sample should still be collected so that there are at least 3 samples post infusion. In all cases the exact time of start and end of infusion and the time of actual sample collection should be noted in the CRF. (as of Amd 1)*

A minimal number of 6 subjects is required. The following parameters will be calculated: C_{max} , AUC, recovery, clearance, MRT and $t_{1/2}$ using non-compartmental methods.

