4.1 General Principles

The statistical evaluation will be performed by using the software package SAS release 9.2 or higher (SAS Institute Inc., Cary, North Carolina, United States). All data will be listed and summary tables will be provided. The number of data available and missing data, mean, standard deviation, and other summary statistics will be calculated for continuous data. Frequency tables will be generated for categorical data. Unless otherwise noted, any statistical tests will be 2-sided and performed at the 0.05 significance level.

Standard programs such as ADMAP and MOSTO will be used.

There will be a Validity Review Meeting and it is possible that this SAP might be updated based on the Validity Review Report.

The primary variable is the annualized number of total bleeds (sum of spontaneous bleeds, trauma bleeds, untreated bleeds, and 'other' bleeds) that occur within 48 hours after all prophylaxis infusions. [Note this is a change from the protocol that defined total bleeds to be the sum of spontaneous bleeds and trauma bleeds.]

Secondary efficacy parameters are:

- Annualized number of total bleeds (sum of spontaneous bleeds, trauma bleeds, untreated bleeds, and 'other' bleeds) during prophylaxis treatment
- Hemostatic outcome of surgeries (both major and minor) including blood loss, transfusion, and/or hemostatic-related surgical complications
- FVIII recovery values
 [note: recovery = (post-infusion FVIII pre-infusion FVIII) * body weight / IU]

Additional efficacy parameters are:

- Annualized number of joint bleeds, spontaneous bleeds, and trauma bleeds that occur within 48 hours after all prophylaxis infusions
- Annualized number of joint bleeds, spontaneous bleeds, and trauma bleeds

- % of joint bleeds in target joint for subjects with target joint
- Number of infusions for the treatment of bleeds per bleed
- For all infusions and prophylaxis infusions, FVIII usage calculation expressed in number of infusions, IU, IU/kg, IU/infusion, IU/year, IU/kg/infusion, and IU/kg/year.
- For bleed infusions, FVIII usage calculation expressed in number of infusions, IU, IU/bleed, IU/kg/bleed, IU/bleed (first infusion), IU/kg/bleed (first infusion), IU/infusion, IU/year, IU/kg/infusion, and IU/kg/year.
- For surgery infusions, FVIII usage calculation expressed in number of infusions, IU, IU/kg, IU/infusion, and IU/kg/infusion.
- Description of bleeding according to type, severity, and location as indicated on EPD

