6.5 Additional analyses planned to be reported outside the main report

Data from Part B and the extensions will be summarized separatly.

7. Document history and changes in the planned statistical analysis

Version 1.1 03 May 2012 This is the first version of the SAP to be signed off. Previous versions including V1.0 were circulated internally.

Version 2.1 19 Dec 2012 Many minor changes to be consistent with the TLF developed from 3 recent meetings and protocol version 3.0, added ADMAP macro reference, and changed dataset names.

8. References

n/a

A multi-center Phase III uncontrolled open-label trial to evaluate safety and efficacy of BAY 81-8973 in children with severe hemophilia A under prophylaxis therapy

BSP study drug	BAY 81-8973		
Study purpose:	To demonstrate the safety and efficacy of treatment with BAY 81-8973 for prophylaxis and breakthrough bleeds in children with severe hemophilia A		
Clinical study phase:	Phase III	Date:	18Jul2013
Study No.:	13400	Version:	1.0

• Section 4.4, revised text:

The 6 month data for PTPs will be analyzed for regulatory purposes as a final analysis of the main study. This analysis is considered an interim analysis in the protocol because the trial is ongoing in the extension phase and an overall analysis of the whole study is planned after study completion.

• In Sections 4.1 and 6.2, the definition of total bleeds should read as follows:

The primary variable is the annualized number of total bleeds (sum of spontaneous bleeds, trauma bleeds, untreated bleeds, and infusions with reason = other) that occur within 48 hours after all prophylaxis infusions.

• Section 6.2:

All efficacy variables will be summarized using the ITT analysis set. The primary efficacy variable and the FVIII recovery results will also be summarized using the PPS, which will be supportive for the primary efficacy analysis, but will be considered the primary analysis for the FVIII recovery.

Title page

A multi-center Phase III uncontrolled open-label trial to evaluate safety and efficacy of BAY 81-8973 in children with severe hemophilia A under prophylaxis therapy

Leo Kids PUPs (Part B and extension) Interim Analysis

Bayer study drug	BAY 81-8973		
Clinical study phase:	III	Date:	22 Jan 2020
Study No.:	13400	Version:	2.0
Author:	PPD דיט		

Confidential

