6.2 Efficacy

All subjects receiving study drug who have infusion/bleeding data from the EPD will be included in the efficacy analysis.

Primary Efficacy Analysis

The primary efficacy variable according to protocol will be the annualized number of total bleeds (sum of spontaneous bleeds, trauma bleeds, untreated bleeds, and 'other' bleeds) that occur within 48 hours after all prophylaxis infusions. 'Other' bleeds are infusions with reason given as 'other'.

For this primary efficacy variable, the number of data available and missing data, mean, standard deviation (SD), minimum (Min), quartiles, median, and maximum (Max) will be summarized and presented.

Additional Efficacy Analysis

Also summarized will be annualized number of joint bleeds, spontaneous bleeds, and trauma bleeds that occur within 48 hours after all prophylaxis infusions. Additional variables summarized will be annualized number of total bleeds, joint bleeds, spontaneous bleeds, and trauma bleeds as well as the annualized numbers.

Other variables summarized will be the number of treatments required to control all bleeds and the subject's assessment of the response to treatment of all bleeds (excellent, good, moderate, or poor), further on description of joint bleeds according to site as well as proportion of subjects with no bleed

FVIII usage/consumption will be described expressed as number of infusions, number of prophylaxis infusions, and number of infusions to treat breakthrough bleeds. Infusions will be summarized in IU, IU/kg, IU/kg/year, IU/kg/infusion, IU/year, and IU/infusion.

All efficacy variables will be summarized using the ITT analysis set. The summary of bleeds, the exposure to study drug and the treatment administration for bleeds will also be given in the ITT.

The number of infusions used to treat a bleed will be summarized. The number of infusions used to treat a bleed is defined as the first infusion to treat the bleed plus all follow-up infusions to treat the same bleed, if any. The proportion of bleeds controlled by ≤ 2 and ≥ 2 infusions will be presented.

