9.1 Determination of sample size

Due to the fact that the analysis of the efficacy endpoints is exploratory only, no formal determination of sample size was done. The planned number of subjects followed guidelines as well as common practice for this kind of studies.

Title page

Study Protocol Title (incl. version no. and date): A multi-center Phase III uncontrolled open-label trial to evaluate safety and efficacy of BAY 81-8973 in children with severe hemophilia A under prophylaxis therapy (Integrated protocol Version 7.0, 01 Feb 2019)

Leo Kids PUPs (Part B and extension) Interim Analysis

SAP (incl. Version no. and date): Statistical Analysis Plan version 2.0, dated 22 Jan 2020

[Analysis purpose:]	Supplement		
Clinical study phase:	III	Date:	28 JAN 2020
Study No.:	13400	Version:	1.0
Author:	PPD		

Confidential

The information provided in this document is strictly confidential and is intended solely for the guidance of the clinical investigation. Reproduction or disclosure of this document, whether in part or in full, to parties not associated with the clinical investigation or its use for any other purpose without the prior written consent of the sponsor is not permitted.

Throughout this document, symbols indicating proprietary names (®, TM) are not displayed unless quotations from other documents are given. Hence, the appearance of product names without these symbols does not imply that these names are not protected.

This "Additional Statistical Analysis Plan" is produced on a word-processing system and bears no signatures.

Table of Contents

Titl	e page	1
1.	Introduction	3
	Clarifications	
	Secondary Endpoints	

1. Introduction

This SAP Supplement 1.0 is based on the SAP version 2.0. The purpose of this SAP Supplement 1.0 is to align the labeling of the endpoints specified in the SAP 2.0 to the specification described in the SAP for Part A and in the protocol . None of the alignments detailed in this document are considered to change the primary efficacy analysis and other analyses as described in the study protocol and its amendments and in the SAP version 2.0.

2. Clarifications

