2.1 Secondary Endpoints

The secondary parameters are the following:

- Annualized number of total bleeds (sum of spontaneous bleeds, trauma bleeds, untreated bleeds, and 'other' bleeds) during prophylaxis treatment
- Hemostatic outcome of surgeries (both major and minor) including blood loss, transfusion, and/or hemostatic-related surgical complications
- Inhibitor development, as measured by Nijmegen modified Bethesda assay
- FVIII recovery values
- Pharmacokinetics (in a subset of children)

The annualized number of total bleeds will be calculated as described in section 4.5.2 of the SAP 2.0 and summarized accordingly.

The hemostatic outcome of surgeries will presented in a subject listings.

The incidence of inhibitor development during the total part B period will be presented in a summary table, additionally a subject listing will be provided relating the number of total exposure days to the corresponding FVIII Inhibitor value.

The FVIII recovery values will be calculated as described in section 4.7 of the SAP 2.0 and summarized accordingly. In addition, a subject listing will be provided.

The summary of pharmacokinetic values in Part B of the study will only be presented in the final report for the extension study due to the limited number of collected samples.

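### The Part B SAP labels a four-component bleed count as the primary variable 'according to protocol', but the protocol counts only spontaneous and trauma bleeds, and Part B does not disclose the difference

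*SAP*

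**What the plan says.** **Protocol v7.0.** Three current sections agree on two components. Section 4 (Primary variable) has "Annualized number of total bleeds (sum of spontaneous bleeds and trauma bleeds) within 48 hours (h) after a prophylactic infusion". Section 7.3.1 has "total bleeds (sum of spontaneous bleeds and traumatic bleeds) during prophylaxis that occurs" within 48 hours of the last prophylaxis infusion. Section 8.3 repeats "total bleeds (sum of spontaneous bleeds and traumatic bleeds) (as of Amd 1".

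**Part A SAP.** Section 4.1 widens the sum to spontaneous, trauma, untreated and 'other' bleeds and says so openly: "Note this is a change from the protocol that defined total bleeds to be the sum of spontaneous bleeds and trauma bleeds". The Part A supplement of 18 July 2013 confirms four components for Sections 4.1 and 6.2, wording the last ones as "trauma bleeds, untreated bleeds, and infusions with reason = other".

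**Part B SAP v2.0.** Section 1 names protocol v7.0 as its basis. Section 6.2 says: "The primary efficacy variable according to protocol will be the annualized number of total bleeds (sum of spontaneous bleeds, trauma bleeds, untreated bleeds", followed by 'other' bleeds. Sections 4.5 and 6.2 define 'other' bleeds as infusions whose recorded reason is 'other'. Section 6.2 also plans separate summaries of spontaneous and of trauma bleeds within 48 hours.

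**Part B Supplement 1.0 (28 January 2020).** Its aim is to align endpoint labels with the Part A SAP and the protocol. Its secondary total also uses the wider sum: "Annualized number of total bleeds (sum of spontaneous bleeds, trauma bleeds, untreated bleeds", again with 'other' bleeds added.

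**The concern.** A label saying that a variable follows the protocol tells the reader there is no need to check. Here a check would find a different quantity. The sponsor recognised the difference in Part A and disclosed it, and the disclosure did not carry over to Part B.

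The study is uncontrolled and no tests are planned, so the summary statistics for the primary variable are themselves the efficacy result. If the plan is followed as written, the Part B report will present the four-component figures as the protocol's primary variable. The text of the SAP mentions no summary of the two-component sum beside them.

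**Working it through.** The documents give no figure to reproduce, so the check is mainly a comparison of text.

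**1. Components of the primary variable**

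| Source | Spontaneous | Trauma | Untreated | 'Other' | Departure stated? |
|---|---|---|---|---|---|
| Protocol v7.0, 4, 7.3.1, 8.3 | yes | yes | not mentioned | not mentioned | – |
| Part A SAP 4.1 | yes | yes | yes | yes | yes |
| Part A supplement (July 2013) | yes | yes | yes | yes | 4.1 note not withdrawn |
| Part B SAP 6.2 | yes | yes | yes | yes | no; labelled as per protocol |

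The protocol synopsis words the primary variable differently again, in terms of response to treatment. It does not supply the four components either.

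**2. Could a later amendment have adopted the wider sum?** The Part A SAP (v2.1) dates from December 2012. The Part B SAP lists Amendments 4, 6, 7 and 8 as following between April 2014 and February 2019. Protocol v7.0 incorporates all of them and still has two components.

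**3. Is the departure disclosed anywhere in the Part B documents?** Section 4.5 lists the four components without comment. The change history in Section 7 does not mention the definition. Supplement 1.0 does not mention a difference.

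**4. Which components are additions?** The treatment log in protocol Section 7.3.2.2 has 'other' as a reason separate from first treatment of a spontaneous or a trauma bleed. Counting those infusions as bleeds is therefore an addition. Untreated bleeds are less clear, because the protocol does not say that a bleed must be treated to count.

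**5. Scale (illustration only).** One extra counted bleed adds 365.25/T to a child's annualized total, with T the days in the analysis period.
- T = 365.25: 365.25/365.25 = 1.0
- T = 182: 365.25/182 = 2.0
- T = 70 (assumed: leaves after 20 exposure days at two per week): 365.25/70 = 5.2

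Early leavers are annualized too (Part B SAP 4.2), so none of these is a bound.

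An assumed child with one event of each of the four types over 182 days, on separate days and all within 48 hours of prophylaxis, has 2 × 365.25/182 = 4.01 per year on the protocol sum and 4 × 365.25/182 = 8.03 on the Part B sum. With no untreated or 'other' events, the two sums agree.

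**6. Direction.** The wider sum will usually give a higher rate, but not always. Under the 24-hour rule (Part B SAP 4.5.3) only one bleed counts per calendar day, and it takes the time of that day's first bleed. Suppose the previous prophylaxis was three days earlier at 09:00. On the day in question there is an 'other' infusion at 08:00, prophylaxis at 09:00 and a spontaneous bleed at 20:00.
- Protocol sum: the bleed is 11 hours after prophylaxis and counts 1.
- Four-component sum: the day's bleed is timed at 08:00, which is 72 − 1 = 71 hours after the previous prophylaxis, and counts 0 in the 48-hour window.

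**7. Can the protocol sum be recovered from the separate summaries?** The mean can, approximately. The median, quartiles and SD cannot. An example with five children:

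| | Rates | Mean | Median | SD |
|---|---|---|---|---|
| Spontaneous | 0, 0, 0, 2, 4 | 1.2 | 0 | 1.79 |
| Trauma | 2, 4, 0, 0, 0 | 1.2 | 0 | 1.79 |
| Sum | 2, 4, 0, 2, 4 | 2.4 | 2 | 1.67 |

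**The case against.** The best defence is that nothing is hidden. Section 6.2 lists the four components in the same sentence as the label and defines 'other'. The label could be read as naming which variable the protocol makes primary, with the parenthesis as the SAP's operational definition. Protocol Sections 7.3.1 and 8.3 leave the full list and detail to the SAP. The wider count is also a sensible convention, since Part B SAP 4.3 recognises bleeds that are neither spontaneous nor traumatic. All of this limits the harm. It does not make the label correct: the protocol states its components, and the Part A SAP calls the same wider sum a change from them.

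A reader might also infer more than the documents support:

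- *That the report will contain no protocol-defined summary.* This cannot be established. Section 1 puts full table details in separate TLF specifications, which were not available to check. Section 4.1 also says individual values will be listed, so a reader with the listings could attempt to rebuild the sum.
- *That Supplement 1.0 declares the two definitions identical.* It says: "None of the alignments detailed in this document are considered to change the primary efficacy analysis and other analyses as described in the study protocol". This statement, which also names SAP version 2.0, covers only the supplement's own alignments, which concern secondary endpoints. The sentence fails to disclose the difference but does not deny it.
- *That the departure is concealed across the whole study.* Part A discloses it, and Supplement 1.0 refers the reader to the Part A SAP. The gap is in the Part B documents.

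**Conclusion.** The label in Part B SAP 6.2 is wrong as written, and the departure from protocol v7.0 is not disclosed in the Part B SAP, its change history or its supplement. This rests on the text alone and needs no assumption about the data.

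The size of the effect on the reported rate is unknown, because no count of 'other' or untreated entries is given. The figures of 1.0, 2.0 and 5.2 per extra bleed are illustrations, and 5.2 depends on an assumed 70-day exit. It would be tempting to conclude that the primary result is inflated or that an efficacy conclusion is at risk. The documents do not support either: the change per entry in the 48-hour count can be positive, zero or negative, and no test or threshold uses the result. Nor do they show that the four-component definition is a poor one. The defect is in how the primary variable is reported, and it should be corrected.

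**What to change.** 1. In Part B SAP 6.2, replace the claim that the definition follows the protocol with the Part A statement that it is a change from the protocol definition. Record this in Section 7.
2. Keep the four-component sum for comparability with Part A. Add a labelled supportive summary, for the total group, of bleeds recorded as spontaneous or trauma within 48 hours of a prophylaxis infusion, with the same summary statistics as the primary variable. Apply the 24-hour and 72-hour rules to those bleeds only, so that an 'other' entry cannot set the time of a counted bleed. Give in a footnote the number of bleeds left out because they were 'other', untreated without a recorded cause, or of missing type.

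The first item costs a wording change. The second costs one additional bleed derivation, because the counting rules must be rerun on the restricted set, and one table row. Both use data already held. A separate listing of 'other' infusions is optional, since Section 4.1 already provides for individual listings.
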